3. STUDY DESIGN

3.1 Overall design

This is a prospective study to evaluate the safety and effectiveness of Sculptra for correction of wrinkles in the décolletage area.

Approximately 30 subjects will be enrolled in the study and randomized 1:1 to receive either Sculptra reconstituted with 8 mL SWFI with the addition of 1 mL 2% lidocaine hydrochloride (HCl) or Sculptra reconstituted with 17 mL SWFI with the addition of 1 mL 2% lidocaine HCl. Subjects will be stratified by GDS severity score (moderate or severe) and study center.

Eligible subjects will perform a screening visit and baseline visit; these visits may be combined, if appropriate. Eligible subjects will be offered treatment with Sculptra in four sessions spaced one month (+2 weeks) apart.

Subjects will be injected with Sculptra by the Treating Investigator at Baseline. Sufficient amount of product, as determined by the Treating Investigator, should be injected to achieve optimal correction, which is defined as at least a one grade improvement on the GDS and best correction that could be achieved as agreed upon by the Treating Investigator and the subject. Three additional treatment sessions may be performed if needed to achieve optimal correction, as determined by the Treating Investigator and subject. Treatment will stop when optimal correction has been achieved and subsequent visits will be follow-up visits.

Effective date: 2022-05-31 12:16

Print date:

Doc id

GALDERMA

initial treatment.

43USSA2112 CIP Sculptra Decolletage

MA-50966

2022-06-13 07:02

Safety follow-up assessments will also be conducted one month after each treatment (Visits 3a, 4a, 5a and 6). Safety and effectiveness data will be collected for up to 9 months following the

Study rationale and justification for design

The purpose of this study is to investigate the safety and effectiveness of *Sculptra* in two different reconstitution volumes for the correction of wrinkles in the décolletage area, with the objective of initiation of a pivotal study.

Evaluations will be performed by the Treating Investigator and the Subject. The intention is to improve the aesthetic appearance compared to baseline. Evaluations will be performed using the validated GDS, validated **CCI** and the GAIS (for Investigators and subjects).

GAIS improvement has been commonly accepted by the medical community in Europe and the United States as clinically meaningful indicator of global aesthetic improvement.

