4.4 Procedures/Reasons for subject discontinuation/withdrawal

Each subject must be advised in the ICF that the subject has the right to withdraw from the study at any time, for any reason, without prejudice. Subjects may also be discontinued from this study if the Investigator determines that it is in the subject's best interest to do so and may be withdrawn at the Investigator's discretion at any time.

The withdrawal criteria are:

Medical Reasons:

If the subject suffers from a medical condition and/or AEs that, in the judgment of the Investigator makes it medically necessary to withdraw the subject. The specific rationale for Investigator-initiated withdrawal of a subject for medical reasons should document the specific condition for withdrawing the subject.

Print date:

2022-06-13 07:02

 Withdrawal by Subject: Includes consent withdrawal, subject relocation, schedule conflicts. A subject can withdraw their consent to participate in the study at their own request or be withdrawn from participation in the study at the request of their legally authorized representative, at any time for any reason.

• Lost to follow-up:

If a subject does not return for a scheduled visit, reasonable efforts shall be made to contact the subject. The subject should only be declared lost to follow-up after confirmation that no responses/answers were obtained from three documented phone calls and a certified letter (receipt of delivery requested).

• Other:

This category is to be used for a subject who discontinues due to a reason other than those specified in the pre-defined categories above. The reason for discontinuation should be explained.

The reason and date for withdrawal should be documented in the subject's source documents and eCRFs. When possible, an explanatory comment should be added to further explain the reason for the withdrawal. If withdrawal of a subject occurs during a regular study visit, the eCRF for that specific visit shall be completed as far as possible.

If withdrawal of a subject occurs between regular study visits, the subject should, when possible, (irrespective of the reason for withdrawal) be scheduled for a termination visit to document the outcome of the secondary endpoints for the subject.

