7.6.5 Pregnancy

Pregnancy itself is not regarded as an AE.

If there is a pregnancy during the study period, the subject must be withdrawn from any subsequent study treatment but should continue to be followed within the study and the outcome of pregnancy must be reported even if the delivery occurs after study completion. Details of pregnancy reporting are outlined in Section 7.8.5.

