7.7 Safety recording instructions

Each subject with an AE occurring after enrollment through study exit should be fully recorded in the source document(s) for further transcription into the eCRF. Each subject should be questioned about AEs at each study visit following randomization and treatment. The question asked should be: "Since your last clinical visit; have you had any health problems?" Information on AEs can also be obtained from signs and symptoms detected during each examination, or from a laboratory test, observations made by the study site personnel, subject diaries, or spontaneous reports from the subjects or their relatives.

When an AE is related to a device deficiency (refer to Section 7.9), including technical device malfunction, the AE shall be recorded on the AE form/module in the eCRF and the technical complaint shall be reported separately on the clinical study complaint form, provided separately in the Investigator file, and the eCRF.

Investigators, or other study site personnel, shall record all AEs in the eCRF, including:

- a) Event term (recorded in standard medical terminology and avoiding abbreviations)
- b) Affected area
- c) Start date (first day with symptoms)
- d) Stop date (last day with symptoms)
- e) Intensity (mild, moderate, or severe according to definition in Section 7.7.1)
- f) Seriousness (serious or not serious, according to definition in Section 7.6.2)
- g) Causal relationship to study product or study product injection procedure (yes or no, see Section 7.7.2)
- h) Action taken (none, medication treatment, non-pharmacological treatment, or other procedures/tests, subject withdrawn)
- i) Outcome of the AE (ongoing, recovered, recovered with sequelae, death, chronic/ stable, not recovered at the end of the study)

The AE form/module in the eCRF must be signed and dated by the Investigator.

The pre-defined, expected post-treatment events shall be assessed separately. These events shall be collected daily by subjects in a diary for up to 28 days after each treatment.

	Title 43USSA2112 CIP Sculptra Decolletage	Doc id
GALDERMA EST. 1981	• 0	MA-50966

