8.2 Visit 2a, Baseline and First Treatment (Day 1) - all subjects

The screening visit and baseline visit (Day 1) may be performed on the same day. *If the screening visit and baseline visit are performed on the same day assessments will not be duplicated.*

Assessments prior to treatment:

- Re-confirm eligibility criteria
- Obtain weight measured at clinic.
- Review for changes in concomitant therapies.
- Perform Urine Pregnancy test for all females of childbearing potential (prior to treatment). Test result must be negative for the subject to be eligible for treatment.
- Record the subject's medical history
- Randomize the subject.

Obtain Photography

•	CCI	
		ı

• GDS assessment – Treating Investigator

Once the subject is deemed eligible for treatment by the Treating Investigator, the following procedures should be completed:

- Sculptra administration
- Evaluate the subject for post-treatment AEs Treating Investigator.
- Evaluate for device deficiencies.
- Dispense diary and instruct subject on daily diary completion. Remind subject to bring the diary to the next on-site visit.

	Title 43USSA2112 CIP Sculptra Decolletage	Doc id
GALDERMA	43055A2112 CIT Sculptra Deconetage	MA-50966

8.2 Visit 3a, Treatment 2/Follow-up (1 month [+ 2 weeks] after Treatment 1) - all subjects

Assessments prior to treatment:

- Re-confirm eligibility criteria.
- Review for changes in concomitant therapies.
- Perform Urine Pregnancy test for all females of childbearing potential (prior to treatment, if applicable). Test result must be negative for the subject to be eligible for treatment.
- Obtain Photography.
- AE assessment.
- Collect subject diary from treatment 1.
- GAIS assessment Treating Investigator and Subject.
- GDS assessment Treating Investigator.
- Schedule the next on-site visit (1 month [+ 2 weeks] after Treatment 2). Treatment and assessments post-treatment, for subjects who receive a second treatment:
- Sculptra administration (optional).
- Evaluate the subject for post-treatment AEs Treating Investigator.
- Evaluate for device deficiencies.
- Dispense diary and instruct subject on daily diary completion. Remind subject to bring the diary to the next on-site visit. (If applicable, if a second treatment is administered.)

[figure not shown]

2022-06-13 07:02

Print date:

Effective date: 2022-05-31 12:16

	Title	Doc id
	43USSA2112 CIP Sculptra Decolletage	200.00
GALDERMA	•	
EST, 1981		MA-50966

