8.12 Visit 7, Follow-up (month 6 [+ 2weeks] after baseline) - all subjects

- Obtain weight measured at clinic.
- Review the subject's concomitant therapies.
- Obtain Photographs.
- Assess for AEs- Treating Investigator

Doc id 43USSA2112 CIP Sculptra Decolletage GALDERMA MA-50966

- GAIS assessment Treating Investigator and Subject.
- GDS assessment Treating Investigator.

8.13 Visit 8/Final visit/Early termination, (month 9 [±2 weeks] after baseline) - all subjects

- Obtain weight measured at clinic.
- Review the subject's concomitant therapies.
- Obtain Photographs.
- Assess for AEs- Treating Investigator

- GAIS assessment Treating Investigator and Subject.
- GDS assessment Treating Investigator.

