#### 2.5.2 Adverse Events (AEs)

All AEs will be coded according to MedDRA and summarized by System Organ Class (SOC), Preferred Term (PT), and treatment. The number of subjects with at least one event, associated percentage, and number of events will be provided.

GALDERMA <small>EST. 1981</small>	Title 43USSA2112 Statistical Analysis Plan - Sculptra Decolletage US PiLot	Doc id MA-55694
---	---	----------------------------------

Effective date: 2023-03-06 14:53

For subject counts, a subject will only be counted once per SOC and once per PT in cases where multiple events are reported for a subject within SOC or PT. For event counts, subjects with multiple events in a category will be counted for each event.

The number of subjects with AEs related to study product or study product injection procedure and unrelated AEs will be presented by SOC, PT, and maximum intensity. Action taken for related AEs will also be summarized by SOC and PT using number of events. AEs related to study product or injection procedure with late onset (> 21 days after most recent treatment session) will be listed.

Serious AEs and AEs of special interest (AESIs) will be listed. **CCI**

For AEs related to study product or study product injection procedure, the number of days to onset and the duration of event will be summarized by SOC and PT using mean, standard deviation, median, minimum, and maximum. Days to onset of an AE will be derived as the start date minus the date of most recent treatment session. Duration of an AE will be derived as the stop date minus the start date + 1. Missing stop date will not be imputed, and therefore no duration will be calculated in these cases.

In addition, a summary of all AEs will be provided, which will include (but is not limited to):

- number of subjects with at least one AE and number of events (in total as well as serious AEs),
- number of subjects with at least one related AE and number of events (in total as well as serious AEs),
- number of subjects with at least one AESI and number of events,
- number of subjects with at least one unrelated AE and number of events (in total as well as serious AEs),
- number of subjects who did not have an AE.

[figure not shown]

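### The adverse event form has no code for injections stopped while the subject stays in the study, so the reason for a skipped session can be recovered only partly

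*Protocol*

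**What the plan says.** Protocol 7.7 item h gives the options for the action taken on an AE: "Action taken (none, medication treatment, non-pharmacological treatment, or other procedures/tests, subject withdrawn". SAP 2.5.2 reports this item for related AEs only, as event counts: "Action taken for related AEs will also be summarized by SOC and PT using number of events".

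Protocol 3.1 fixes the baseline session and allows up to three more if needed. It states when they end: "Treatment will stop when optimal correction has been achieved and subsequent visits will be follow-up visits". The Visit 3a and Visit 4a descriptions in Protocol section 8 list "Sculptra administration (optional", and Visit 5a lists treatment only for subjects who receive a fourth one. All three visits are held for all subjects, treated or not.

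Two sections speak of withdrawal. Protocol 4.4 lists reasons for leaving the study. For AEs the test is the investigator's judgment that the condition "makes it medically necessary to withdraw the subject". Protocol 7.6.5, on pregnancy, says that "the subject must be withdrawn from any subsequent study treatment but should continue to be followed within the study".

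Protocol 1.1 states why the 18 mL total volume is being studied beside the labelled 9 mL: to see whether the larger volume is well tolerated.

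**The concern.** Stopping injections because of an AE while remaining under observation is an ordinary path in this design, and it measures tolerability directly. The action list cannot express it. A site would code the event as *none*, or by how the AE was treated or tested, or as *subject withdrawn* if it read that code as covering treatment. Two sites could code the same event differently.

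If the 17 mL arm receives fewer sessions than the 8 mL arm, that may mean subjects reached optimal correction sooner, or that they tolerated the injections less well. These readings point in opposite directions for the choice of volume in the pivotal study that this pilot is meant to support. The tables listed in the plan would not say which applies.

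**Working it through.** The plan states no figure to reproduce: the sample size is not calculated and no rate of AE-driven stops is given. The check is first a reading of the text, then a small calculation for scale.

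**Step 1. Where could the reason for a skipped session be recorded or reported?**

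- Protocol 7.7 item h: five actions, none meaning that injections stopped and the subject continues.
- Protocol section 8, Visits 3a, 4a and 5a: AEs, the Galderma Décolletage Scale (GDS) and the Global Aesthetic Improvement Scale are assessed. The legible lists do not ask why no injection was given.
- SAP 2.3.1: study withdrawal with its primary reason. A subject who stays in does not appear there.
- SAP 2.5.1: technique, depth, needles, vials, syringes and volume by session. No reason for a session not given is listed.
- SAP 2.5.2: the same action list, for related AEs, counted as events. No table of AEs leading to stopped injections is listed.

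**Step 2. What can be inferred from the other data?** Optimal correction requires at least a one-grade GDS improvement (Protocol 3.1), so the visit GDS helps. Take subjects who have no session 2 but stay in follow-up:

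| Situation at Visit 3a | Action code available | Can the reason be inferred? |
|---|---|---|
| One-grade gain, no AE | not applicable | Probably optimal correction |
| No gain, related AE, untreated | *none* | Not optimal correction; AE likely, but the subject may have declined for another reason |
| One-grade gain, related AE, untreated | *none* | No |
| One-grade gain, related AE, treated | *medication* or similar | No; the code describes the AE's treatment, not the stop |
| Pregnancy | not applicable (not itself an AE) | Yes, from the pregnancy report |

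The two rows with both a gain and an AE stay unresolved. The second row is settled only by reading listings.

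**Step 3. Scale.** Approximately 30 subjects randomized 1:1 gives an assumed n = 15 per arm. The intervals are Clopper-Pearson, the SAP's method for its response rates.

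- 0 stops shown: upper limit = 1 − 0.025^(1/15) = 21.8%.
- 1 stop shown: 1/15 = 6.7%; lower limit = 1 − 0.975^(1/15) = 0.2%; the upper limit solves (1 − p)^15 + 15p(1 − p)^14 = 0.025, giving p = 31.9%.

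Missing one stop therefore moves an arm from 1/15 (0.2 to 31.9) to 0/15 (0 to 21.8).

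The chance that at least one such stop occurs among 30 subjects is 1 − (1 − r)^30, with the rate r assumed:

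| Assumed r | At least one among 30 | At least one in an arm of 15 |
|---|---|---|
| 2% | 45.5% | 26.1% |
| 5% | 78.5% | 53.7% |
| 10% | 95.8% | 79.4% |
| 15% | 99.2% | 91.3% |

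**The case against.** The strongest reply is that the information is largely there. GDS and AEs are assessed at each visit where a session can be skipped. AE dates, intensity and causality are recorded, vials and volume are summarized per session, and all data are listed by subject. With about 30 subjects a reviewer can read every line. This stands in part: as Step 2 shows, some stops can be explained from the data and others cannot.

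A second reply is that absence cannot be proved here. The eCRF is not among the documents. The treatment procedure, the study stopping rules, the schedule of assessments and parts of the SAP safety section are redacted or missing. A reason field or a table may exist there. This stands, and it limits the point to the legible text. A field in the eCRF alone would still not supply the missing code in 7.7 h.

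A reader might also infer more than the documents support:

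- *That an AE-driven stop forces study withdrawal.* It does not. Withdrawal under 4.4 rests on the investigator's judgment, and later visits are held for all subjects.
- *That 4.4 and 7.6.5 contradict each other.* They govern different events: leaving the study, and stopping treatment within it. Only the shared word makes the code in 7.7 h ambiguous.
- *That such a subject is counted as a success.* Fewer sessions may look like early correction in the exposure record, but response is the Month 9 GDS change, whatever the number of sessions.
- *That she is scored as a Month 9 failure.* Baseline carried forward applies only if the Month 9 GDS is missing, and observed-case, worst-case and best-case analyses are planned. The loss of 1/15 = 6.7 points (for example 12/15 = 80.0% to 11/15 = 73.3%) would follow from any would-be responder with a missing value, so it does not measure this gap.

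**Conclusion.** The point holds as a gap in data capture and reporting. The legible plan lets a subject stop injections and stay in the study, gives the AE form no way to say so, and lists no table of why sessions were not given. A difference in sessions between arms could be explained only partly, by inference from visit GDS, AE dates and listings. This weakens the tolerability comparison that Protocol 1.1 gives as the reason for studying the larger volume.

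The effect is small in absolute terms but not trivial at this sample size: one uncaptured stop is the difference between 0/15 and 1/15 in an arm. That rests on an assumed 15 per arm. How often such stops occur is unknown, and the rates from 2% to 15% are assumptions. The primary effectiveness result is not at risk from this gap alone. The conclusion would weaken if the unseen eCRF or redacted text already records the reason. This is an inexpensive improvement to a descriptive pilot, not a flaw that invalidates it.

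**What to change.** 1. In Protocol 7.7 h, add an action code meaning no further study injections with the subject continuing in the study, and reword the existing code as withdrawn from study.
2. If the eCRF does not already have it, add one field at Visits 3a, 4a and 5a, completed when no injection is given: optimal correction, AE, subject declined, pregnancy, other.
3. In SAP 2.5.1 and 2.5.2, tabulate these reasons, and the AEs leading to stopped injections, by arm and session.

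The cost is a minor eCRF, protocol and SAP amendment, with no added visits. The reason is best recorded when the decision is made, since later reconstruction meets the ambiguity described above. These changes concern recording only. They propose no rule for when injections should stop, which remains with the sponsor and the investigator.

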7.7.1 Assessment of Intensity

Intensity will be recorded for each reported AE. The following definitions of intensity must be used:

Mild: Awareness of symptoms or signs, but easily tolerated (acceptable)

Moderate: Enough discomfort to interfere with usual activity (disturbing)

Severe: Incapacity to work or to do usual activity (unacceptable)

If the intensity changes within one day, the maximum intensity of the AE during that day must be recorded.

7.7.2 Assessment of Causal relationship and Seriousness

Each AE, serious as well as non-serious, shall be assessed by the Investigator for causal relationship with the study device and its use (the injection procedure) and for seriousness (Yes or No) of the event.

A two-point scale ("Yes" or "No" response) shall be used for the causality assessments. The Investigators shall be asked to indicate a response to each of the following questions in the eCRF:

- "Do you consider that there is a reasonable possibility that the event may have been caused by the study device?", and
- "Do you consider that there is a reasonable possibility that the event may have been caused by the study device injection procedure?"

If any of these questions is answered with "Yes", the AE is considered related.

Each AE will also be assessed for causal relationship and seriousness by the Sponsor, in order to fulfil regulatory requirements.

7.8 Safety reporting procedures and timelines

7.8.1 Reporting of Adverse Events (AE)s

AE reporting on each subject shall start upon randomization. The reporting shall continue during each follow-up visit (including telephone contacts and extra visits between planned visits) until the last scheduled visit in the study. All AEs, non-serious as well as serious, must be reported as an AE in the eCRF.

Any events that occur after the subject signs the ICF, but before randomization, will be recorded in the subject's medical history.

7.8.2 Reporting of Adverse Events of Special Interest (AESIs)

Appropriate follow-up should be conducted in order to determine the cause, severity, seriousness, outcome, and relationship to the study device or procedures. In case of difficulty obtaining all the required information within 24 hours, an initial report can be submitted, with follow-up information provided within 24 hours of awareness of the new information.

[figure not shown]
The following information should be provided when reporting an AESI:

- Study Number CTN 43USSA2112
- Subject identification (age, subject number and initials)
- Date and time when the AE occurred
- Adverse event description
- Medical history related to the event
- Treatment specification
- Seriousness of the event
- Relatedness to study device or procedure
- Event outcome (with resolution date and time, if applicable)
- Prior exposure to similar device
- Investigations performed as a result of the AE
- Interventions for treatment of the AE
- Name and signature of Investigator

If the Investigator assesses an AESI to be serious, an SAE report should be submitted as specified in Section 7.8.3.

Upon receipt of the AESI report, the Medical Monitor and Sponsor will review the information provided, assess the event, and report as applicable to RA and IRB.

The SAE form must be signed and dated by the Investigator. If the initial 24-hour SAE report does not contain full information, or if it is made without using the SAE form, the fully completed and signed SAE form shall be e-mailed to the CRO. A copy of the fully completed SAE form shall be kept at the site.

In addition, the Investigator shall report SAEs to the responsible IRB without undue delay. The Investigator is responsible for checking what reporting procedures are applicable for his/her IRB regarding SAEs and final report of the outcome of the study and to comply with such reporting procedures during the study period.

The Sponsor is responsible for reporting to the RA, if applicable and according to national regulations.

